2.1 The effect of protein intake on appetite and satiety

Bariatric surgery is the most effective method of maintaining long-term weight loss in patients with morbid obesity and for treating Type 2 Diabetes. Understanding the physiological changes after bariatric surgery has been challenging as many factors are implicated at different levels with extremely variable magnitude of effects. Following the operation patients generally prefer meals with higher protein content but lower fat and carbohydrate contents. Decrease in appetite has been described following oral application of high protein containing meals in obese patients. Dietary proteins are generally described as the most satiating nutrient. Diets high in protein have been shown to be a potential tool for weight loss. Recent studies have shown that proteins have more satiating effect than carbohydrates, which in turn are more satiating than fats.

Cholecystokinin (CCK) reduces food intake and meal size and induces satiety in a variety of mammalian species rats and humans [1]. Glucose-dependent insulinotropic polypeptide (GIP) and glucagon-like peptide-1 (GLP-1) are a key incretin secreted from enteroendocrine cells in the intestinal epithelium in response to an oral nutrient load. GLP-1 is synthesized and secreted by enteroendocrine L-cells which are expressed over a large portion of the GI tract, starting in the proximal small intestine and progressively increasing in density down to the distal part of the colon. PYY is present throughout the intestinal tract, with the highest concentrations in distal segments [2]. Two forms are released postprandially: PYY1–36 and PYY3–36 [3] [4], but the latter has the most potent anorectic effects when administered peripherally [5]. Several hormonal signals, including PYY, are generated during a meal, and it has been suggested that several of these signals may contribute to satiety. Recent studies have advocated a significant physiological role for PYY as a regulator of energy homeostasis and demonstrated that it mediates the satiating and weight reducing effects of dietary protein. PYY release from the intestinal tract may be inhibited in the obese, thus leaving obese subjects with a functional deficiency in PYY-induced satiety. Obese subjects have a PYY deficiency that would reduce satiety and could thus reinforce their obesity [6]. Food induced activation of gut peptides such as peptide YY (PYY) and Glucagon-Like Peptide- 1 (GLP-1) is known to reduce food intake and hunger feelings in humans [7]. The secretion of GLP-1,

CCK and peptide YY (PYY) seem to be increased in response to a high-protein diet whereas concentrations of ghrelin seem to be reduced [8] [9] [10]. The responses of the gut hormone peptide YY (PYY) to food were investigated in 20 normal-weight and 20 obese humans in response to six test meals of varying calorie content concluded that obese subjects have a PYY deficiency that would reduce satiety and could thus reinforce their obesity. In the postprandial PYY study, obese volunteers had a significantly lower fasting PYY than the normal-weight subjects. Plasma PYY peaked 90 min after the meal was ingested. A graded rise in peak plasma PYY was observed for both normal-weight and obese subjects in response to increasing calorific meals. Obese subjects, however, had a lower peak PYY response than normal-weight subjects for each calorie load. Thus, approximately double the meal calorie content was required to achieve equivalent PYY levels to those observed in normal-weight subjects. Moreover, this lower PYY level in the obese subjects was matched by a lower level of fullness after the 1000, 2000, and 3000-kcal meals as measured by VAS. The difference was significant at 30 min and was sustained until 180 min postprandially. The PYY response after 1000 kcal was not significantly different in the 500- and 900-ml protocols, evidence against a significant effect of volume on PYY response (Figure 1)

[figure not shown]

Figure 1: C, peak PYY levels in obese (●) and normal-weight (○) subjects at 90 min after the meal; D, fullness scores at 180 min after the meal, measured by VAS in the obese (●) and normal-weight (○) subjects. $P < 0.05$ (unpaired t test).

An investigational study on normal and obese human subjects found that high-protein diet caused the greatest reduction in hunger in both age-matched normal-weight and obese male volunteers. The high-protein meal resulted in the greatest increment in both total plasma PYY and integrated PYY levels in both groups, although post-meal levels were lower in obese subjects (Figure 2)

[figure not shown]

Figure 2: Hunger scores and PYY levels in normal weight and obese human subjects following high protein, high-fat, and high-carbohydrate isocaloric meals A and B) Time course of subjective visual analogue scale ratings (mm change from baseline) for hunger in normal-weight subjects (A) and obese subjects (B) after ingestion at time 0 of isocaloric meals. C and D) Time course of plasma PYY levels in normal-weight subjects (C) and obese subjects (D) after ingestion at time 0 of isocaloric meals. E and F) Area under curve (AUC) for PYY3-36 release in normal-weight subjects (E) and obese subjects (F) after ingestion at time 0 of isocaloric meals. * $p < 0.05$, ** $p < 0.01$, *** $p < 0.001$. PROT = high-protein; CHO = high-carbohydrate; FAT = high-fat. All values represent group mean \pm SEM, $n = 10$ for normal weight subjects, and $n = 9$ for obese subjects.

Dietary proteins are generally described as the most satiating nutrient, an effect that may be partly mediated by the stimulation of anorexigenic GI peptides secretion, including that of GLP-1. It was demonstrated that the satiating effect after a high-protein preload was significantly larger than preloads containing an iso-energetic amount of carbohydrates or fats [11] [12]. The recent expert opinion on recommended dietary allowance (RDA) for protein in older adult's ranges from 1.0 – 1.2 g/kg/d [13].

Most proteins cannot be delivered orally due to problems related to degradation in the acidic environment of the gastrointestinal tract. Most previous studies used catheters for the delivery of macronutrient. Parenteral administration of proteins has now become more common practice for daily protein administration. For oral protein supplements it is necessary to maintain protein bioactivity during microspheres or microcapsules formation as much as possible to induce maximal stimulatory effect on gut hormones. Encapsulation is a physico-chemical or mechanical process whereby bioactive components are completely enveloped by a matrix for physical protection against potentially hazardous processes and adverse environmental conditions. The capsules are also classified as a food substance as they have a pure protein matrix that contains no synthetic elements and allows controlled disintegration due to intestinal digestion.

The goal of the present study is to investigate the physiological effect of natural macronutrients when delivered exogenously to the proximal and distal small bowel. This will mimic some aspects of the physiological changes after Roux-en-Y gastric bypass. The oral administration of macronutrients in a protective capsule will enable us to deliver them to the proximal or the distal part of the small intestine depending on the chemical and physical properties of the capsules. Our study will provide important information on the physiological role of protein, fat, and carbohydrate content of the ingested food on specific gut hormone secretion and their effects on satiety

3 Potential side effects and risks

Blood sampling can cause mild pain and/or bruising. A doctor or a trained phlebotomist will insert this with experience in obtaining blood samples to minimise the discomfort caused. We do not expect any severe side effects

4 Study hypothesis

The delivery of high protein supplement to the proximal and distal gut will increase the release of anorexigenic gut hormones that have powerful satiety effect and will reduce food intake.

5 Study Objectives and Design

5.1 Primary Aim:

To identify the physiological satiety gut hormone response and the satiety response of subjects when macronutrients are digested in the distal rather than proximal small bowel.

5.1.1 Objective 1:

To quantify the physiological gut hormones response of differential macronutrient delivery to the proximal and distal small bowel.

5.1.2 Objective 2:

To quantify the physiological satiety response of differential macronutrient delivery to the proximal and distal small bowel.

5.1.3 Objective 3:

To quantify the amount of food consumed after a preload of differential macronutrient delivery to the proximal and distal small bowel.

5.2 Study design

This is a randomized six-way crossover study. The study will include 10 healthy volunteers with each subject being studied on six separate occasions at weekly intervals (Figure 3).

[figure not shown]

Figure 3: Schematic of Study Design

5.3 Primary endpoint

Changes in appetite as measured by visual analogue scale

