5.4 Secondary endpoints

Changes in gut hormone concentrations as indicated by serum levels of these hormones

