5.5.3 Study procedures

At the screening visit a doctor or nurse will then perform the following tests and procedures to determine if the subject is eligible for the study:

- Medical history
- Physical examination
- Body measurements including height, weight and waist circumference
- Record of your medications or illnesses
- Urine pregnancy test (if applicable)

Visit 1-6 (1 week apart):

Subjects will be randomised to consume a one the 6 microcapsules in each week. Internet-based randomisation software will be used to allocate microcapsules to each subject at each visit

Eligible subjects will be invited to six consecutive visits in the clinical research centre at St Vincent University Hospital. On each occasion we would request you to have identical meals the night before between 19:00 and 20:00 hours and fast thereafter. Please refrain from alcohol and strenuous exercise for 24 hours before each study visit.

1. Food intake for the 24 h before each study day should be similar.
2. Participants will be asked to consume an identical meal between 19.00 and 20.00 on the night before each study (fish or pasta meal).
3. They will also be asked to be fasted and drink only water from 20.00 the night before the study.

In each visit, participants will be asked to be in the clinical research centre at 8:30. At 9:00 am a cannula will be inserted into the antecubital vein of the forearms. About 5 mL (1 teaspoon equivalent) will be taken to measure baseline hormone level. Another blood samples will be taken every 30 minutes thereafter. At 12:00, a final blood sample will be withdrawn and the cannula will be removed (total blood samples 7). They will be asked to answer a questionnaire regarding your feeling of hunger, satiety and if there is any nausea on a linear scale. Then a drink containing 200 grams of macronutrient microcapsules suspension equating to 1087 kcal will be offered. At 12:00 an *ad libitum* meal will be offered. After the meal they will also be provided with a similar questionnaire to fill in, in order to establish your fullness and satiety level. The total visit time is around five hours and there is a total of approximately 35 ml of blood (less than 2 table spoons) at each visit 1 to 6.

6 Methodology

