Data will be analysed using GraphPad Prism (version 6.0) for Windows, GraphPad software (San Diego, CA, USA) and SPSS® (version 20.0) software (SPSS, Chicago, IL, USA). Central tendencies for patient and control group demographics, anthropometric data, caloric intake, VAS scores, QoL scores and macronutrient intake will be calculated and expressed using arithmetic mean \pm standard error of the mean or median (range), as appropriate. Differences in continuous variables between surgical and control groups will be calculated using the Student's *t* test or Mann-Whitney U test for parametric or non-parametric data, respectively. Correlative analyses will be performed using the Spearman Rho rank correlation to assess the relationship between *ad libitum* caloric intake and macronutrient intake with peri-operative weight loss and anthropometric data. Univariate analysis of factors associated with perioperative and post-surgical weight loss will be performed using Student's *t* test or one-way ANOVA for categorical variables or simple logistic regression for continuous variables. For the multivariate analysis, independent variables which were significant on univariate analysis, including standard demographic, oncologic and operative parameters as well as food intake and food preference, will be entered into a multiple logistic regression model with a forward stepwise selection procedure to assess their impact on perioperative and post-surgical weight loss. All statistical analyses will be two-tailed with the threshold of significance set at $P < 0.05$. Caloric intake and visual-analogue scores within groups will be compared by the Wilcoxon signed rank, matched-pairs test. Areas under the curve and plasma hormone levels will be compared by Wilcoxon rank-sum analysis.

12 Duration of Project

The estimated duration of the study will be 12 months. Screening and recruitment will begin in May 2017. Completion of the study is planned for May 2018.

13 Administrative considerations

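### The endpoints are described only as changes, and the pre-drink baseline collected at every visit is not used as a covariate in any planned analysis

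*Combined protocol and SAP*

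**What the plan says.** Section 5.3 gives the primary endpoint as "Changes in appetite as measured by visual analogue scale". Section 5.4 gives the secondary endpoint as "Changes in gut hormone concentrations as indicated by serum levels of these hormones". Neither states a reference point, a time point, a VAS item or a summary measure.

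Section 5.2 sets the design: "This is a randomized six-way crossover study", with 10 subjects seen weekly. At each visit, section 5.5.3 takes a first blood sample: "About 5 mL (1 teaspoon equivalent) will be taken to measure baseline hormone level". Sampling then continues every 30 minutes to 12:00. Before the drink there is also a questionnaire: "They will be asked to answer a questionnaire regarding your feeling of hunger, satiety and if there is any nausea on a linear scale". The only later questionnaire described in that section follows the ad libitum meal offered at 12:00: "After the meal they will also be provided with a similar questionnaire to fill in, in order to establish your fullness and satiety level".

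Section 11 plans this for intake and VAS: "Caloric intake and visual-analogue scores within groups will be compared by the Wilcoxon signed rank, matched-pairs test". Areas under the curve and hormone levels are to be compared by the rank-sum test. Section 11 names no change score, no baseline covariate, and no model with subject and visit effects.

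**The concern.** The plan pays for a baseline at each of the 60 visits (10 subjects × 6) and then does not say how it enters the analysis. Two readings are open. Under one, the visit's baseline is subtracted and raw changes are compared. Under the other, post-drink scores, levels and areas are compared and the baseline is ignored.

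In a crossover, the within-subject comparison already removes stable differences between people. The visit's own baseline therefore helps only through the correlation left within a subject from visit to visit. Meals and fasting before each visit are standardised, so that correlation may be low (an assumption). If it is low, subtracting the baseline adds noise. If it is high, ignoring the baseline wastes information. Using it as a covariate lets the data set the weight. With 10 subjects, the choice can matter for the distal-minus-stomach comparison. It should also be fixed before the data are seen, because three defensible analyses left open invite selection among them.

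**Working it through.** **The plan's own figure.** Section 5.5 gives n = 10 at 80% power and alpha 0.05, with ad libitum energy intake as endpoint. It states no effect size, SD or test, so the figure can only be solved backwards: a two-sided paired t test with 10 pairs needs a standardised within-subject difference of 0.996. Intake has no pre-drink baseline, so this calculation is untouched by what follows.

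**Inputs.** From the documents: 10 subjects, 6 visits, one pre-drink value per visit. Assumed, because the documents give neither: r, the within-subject, same-visit correlation of pre- and post-drink values, and k, the pre-drink SD divided by the post-drink SD (both within subject).

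**Variance of a drink contrast, relative to comparing post-drink values only**

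- Post-drink value only: 1
- Raw change: 1 + k² − 2rk, which is 2(1−r) when k = 1
- Baseline as covariate: 1 − r², before the cost of estimating the slope

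Raw change minus adjusted is (1 + k² − 2rk) − (1 − r²) = (k − r)², which is never negative. Post-only minus adjusted is r², also never negative. So, apart from the slope cost, adjustment has no larger variance than either alternative for any r or k. At k = 1, adjusted over change is (1−r²)/[2(1−r)] = (1+r)/2.

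| r | change / post-only (k=1) | adjusted / change (k=1) | adjusted / post-only |
|---|---|---|---|
| 0 | 2.00 | 0.50 | 1.00 |
| 0.3 | 1.40 | 0.65 | 0.91 |
| 0.5 | 1.00 | 0.75 | 0.75 |
| 0.7 | 0.60 | 0.85 | 0.51 |
| 0.9 | 0.20 | 0.95 | 0.19 |

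**Sensitivity to equal SDs.** At k = 0.5, adjusted over change is 0.91/0.95 = 0.96 at r = 0.3, 0.75/0.75 = 1.00 at r = 0.5, and 0.51/0.55 = 0.93 at r = 0.7. Most of the gain over raw change then disappears. The adjusted/post-only column does not depend on k.

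**Cost of the slope.** With subject, visit and drink effects, the residual degrees of freedom are 60 − 1 − 9 − 5 − 5 = 40, or 39 with the covariate. For a normally distributed baseline, the variance is inflated by (ν−1)/(ν−2), where ν is the residual degrees of freedom before the covariate. With ν = 40 this is 39/38 = 1.03. For one isolated 10-pair comparison, ν = 9 and it is 8/7 = 1.14.

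**Simulation** of the full model (10 subjects, 6 visits, random drink orders, k = 1, 3,000 runs per setting), which includes the slope cost:

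| r | adjusted / change | adjusted / post-only | power for a 1-SD difference: change, adjusted, post-only |
|---|---|---|---|
| 0 | 0.225/0.442 = 0.51 | 0.225/0.220 = 1.02 | 30%, 53%, 54% |
| 0.3 | 0.206/0.316 = 0.65 | 0.206/0.221 = 0.93 | 41%, 56%, 53% |
| 0.5 | 0.167/0.219 = 0.76 | 0.167/0.223 = 0.75 | 54%, 65%, 55% |
| 0.7 | 0.117/0.135 = 0.87 | 0.117/0.220 = 0.53 | 77%, 80%, 54% |
| 0.9 | 0.044/0.045 = 0.98 | 0.044/0.219 = 0.20 | 99.6%, 99.5%, 54% |

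With no true difference and r = 0.5, the adjusted model rejected in 5.5% of runs and the change score in 4.6%.

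**The case against.** A reader might infer that the plan defines its endpoints as raw changes from baseline. The documents do not support that. Sections 5.3 and 5.4 never say from baseline, and section 11 subtracts nothing. So the (1+r)/2 ratios, and any statement that 10 adjusted subjects are worth about 15, 13 or 12 analysed by change scores (10/0.65, 10/0.75, 10/0.85), hold only if raw changes are what is meant and the SDs are equal. Against the scores that section 11 appears to compare, the factor is 1−r², and the gain is smallest exactly where r is low. For hormones, an area under the curve and a single baseline concentration have different units, so the equal-SD formula does not apply; 1−r² still does. All of this stands and limits the size of the claim.

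It is also tempting to call the adjustment free. It is not. Wilcoxon tests take no covariate, so the method of analysis has to change. In a single 10-pair comparison the 8/7 factor makes adjustment worse than post-only at low r (1.14 at r = 0; 0.91 × 8/7 = 1.04 at r = 0.3) and worse than raw change above about r = 0.75. That penalty does not carry over to one model for all 60 visits, where the cost is 2 to 3% of variance.

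Finally, the only VAS described after the drink follows the ad libitum meal, so it may reflect intake, which is itself an outcome (Objective 3). Which item and reading form the endpoint has to be settled before the form of adjustment matters. This stands, and belongs in the same edit.

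**Conclusion.** The point holds in a limited form. The endpoints are described only as changes, the stated analysis does not match that description, and a baseline available at every visit has no stated role. In a linear model over all six visits, using it as a covariate is the safe choice under either reading: apart from 1 of 40 residual degrees of freedom, its variance is no larger than that of raw change or post-only.

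The size of the gain is not known. It depends on r and, for the comparison with raw change, on the SD ratio. It runs from nothing (a loss of about 2% in variance at r = 0 against post-only) to a variance ratio of 0.75 at r = 0.5 against either alternative with equal SDs. This is a matter of precision and pre-specification. It does not show bias in the comparison, and it does not bear on n = 10. The change is worth making but is not critical.

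**What to change.** In 5.3 and 5.4, state which VAS item and which already planned post-drink reading is the primary endpoint, and name the hormone summary, for example the 0–180 minute area under the curve.

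In section 11, analyse each in a linear crossover model over all six visits, with subject, visit and drink effects and that visit's pre-drink value as a pre-specified covariate. Use fixed subject effects. Add the subject's mean baseline only if subject is random; with fixed subject effects that term is redundant and cannot be estimated. Report the adjusted distal-minus-stomach difference with a 95% confidence interval, and show raw changes descriptively.

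Cost: text in three sections, 1 of about 40 residual degrees of freedom, and a model-based analysis in place of the Wilcoxon tests for these endpoints. No new data are needed, and the sample size is unchanged.

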5.4 Secondary endpoints

Changes in gut hormone concentrations as indicated by serum levels of these hormones

5.5 Study subjects

10 healthy volunteers of both sexes age 18 to 65 years will be recruited. Power analysis with amount energy ingested *ad lib* as endpoint indicate need for n=10 at power 80% and alpha of 0.05.

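### The only power figure (n=10, 80%) is for ad libitum intake, not for the declared VAS primary endpoint; its inputs are missing and no primary contrast is named

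*Combined protocol and SAP*

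**What the plan says.** Section 5.2: "This is a randomized six-way crossover study". The Summary lists six meals: high protein, high fat and high carbohydrate (CHD), each in capsules that break down in the stomach or in the distal small bowel.

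- **Aim and objectives.** The Primary Aim (5.1) concerns hormone and satiety responses "when macronutrients are digested in the distal rather than proximal small bowel". Objective 3 (5.1.3) is "To quantify the amount of food consumed after a preload of differential macronutrient delivery" to the proximal and distal small bowel.
- **Endpoints.** Primary (5.3): "Changes in appetite as measured by visual analogue scale". Secondary (5.4): "Changes in gut hormone concentrations as indicated by serum levels of these hormones". Ad libitum intake is in neither list.
- **Sample size (5.5).** "10 healthy volunteers of both sexes age 18 to 65 years will be recruited". The power analysis openly takes ad libitum energy intake as its endpoint and is said to "indicate need for n=10 at power 80% and alpha of 0.05". Nothing more is given.
- **Analysis (11).** All tests are two-tailed at P<0.05. Caloric intake and VAS scores are compared within groups by signed-rank; areas under the curve and hormone levels by rank-sum. The groups it names are surgical and control. It names no primary comparison and no multiplicity rule.
- **Losses.** Section 7.1 lists reasons for withdrawal. Section 6.4.1 provides for deletion of a subject's information when consent is withdrawn.

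**The concern.** A power statement tells the reader what the trial can detect on the result that decides it. Here that result is VAS appetite, and the power statement is about something else. A null VAS finding would be hard to interpret, because no detectable VAS effect is stated.

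The second issue is choice. Six meals give 15 possible pairs. The Primary Aim gives a direction (distal versus proximal) but no analysable contrast. Section 4 does not settle it either: "The delivery of high protein supplement to the proximal and distal gut will increase the release of anorexigenic gut hormones" names both sites without predicting a difference between them. With every test at 0.05 and none designated as primary, the main result could be picked after the data are seen.

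Third, the number recruited equals the number said to be needed, so any loss lowers the power unless subjects are replaced. The plan does not say whether they are.

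**Working it through.** **Inputs from the document.** n=10, power 80%, alpha 0.05 (5.5); two-sided testing (11); six meals per subject (5.2). Not given: difference, SD, contrast, test. The correlations and the 1.0 SD effect below are assumptions, and differences are taken as normal.

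**1. Can n=10 be reproduced?** No, because the inputs are missing. One can only solve backwards for the effect that n=10 would need. For a paired t test with 9 df, noncentrality is d√10, where d is the mean difference divided by the SD of the paired differences:

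- two-sided 0.05, paired t: d = 0.996
- one-sided 0.05, paired t: d = 0.853
- two-sided, pooled crossover error (df = 60−1−9−5−5 = 40), one pair of meals: d = 0.908
- the same error, distal versus stomach averaged over three macronutrients: 0.524 single-pair SD

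Each of these fits n=10 with a different effect.

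**2. What ten subjects detect in one paired two-sided 0.05 comparison.** Exact two-sided signed-rank sizes are 50/1024 = 0.0488 (n=10), 20/512 = 0.0391 (n=9) and 10/256 = 0.0391 (n=8).

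| Completers | 80% power, paired t | 80% power, signed-rank | Power at 1.0 SD, paired t | Power at 1.0 SD, signed-rank |
|---|---|---|---|---|
| 10 | 1.00 SD | 1.02 SD | 80% | 78% |
| 9 | 1.07 SD | 1.15 SD | 75% | 68% |
| 8 | 1.16 SD | 1.25 SD | 68% | 61% |

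The steeper signed-rank loss is partly discreteness: the attained size drops from 0.0488 to 0.0391.

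**3. False positives if the three distal-versus-stomach pairs are each tested by signed-rank, unadjusted.** For independent differences, 1−(1−0.0488)³ = 13.9%. Simulation gives 14.0%, 13.8%, 13.5% and 12.8% at assumed correlations of 0, 0.2, 0.3 and 0.5 between the paired differences. That is about 13-14% per outcome.

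**4. The same for one hormone measure by rank-sum.** The exact size for 10 versus 10 is 4.3%, so at zero correlation 1−(1−0.043)³ = 12.4%. Rank-sum ignores the pairing, so its size falls as within-subject correlation rises. For three contrasts the chance is about 12%, 6%, 3% and 0.6% at assumed within-subject correlations of 0, 0.3, 0.5 and 0.7. Section 6.6.1 names two hormones and each visit has seven samples, so more measures or time points would raise it.

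**5. Averaged or single primary contrast?** The SD of a subject's mean of three differences is √((1+2r)/3) single-pair SD: 0.577, 0.683, 0.730 and 0.816 at r = 0, 0.2, 0.3 and 0.5. Signed-rank power with ten completers and an assumed 1.0 SD effect:

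| r | Average, all three respond | Average, only protein responds | Protein pair |
|---|---|---|---|
| 0 | 99.7% | 36% | 78% |
| 0.2 | 98% | 27% | 78% |
| 0.3 | 96% | 24% | 78% |
| 0.5 | 92% | 20% | 78% |

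**The case against.** Intake is not foreign to the plan. It is Objective 3 under the Primary Aim, and section 5.5 says plainly which endpoint it powers. That stands: the defect is a mismatch between objectives, endpoints and power basis, not a concealed or irrelevant calculation.

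A reader might infer that n=10 is too small or miscalculated. The documents do not support that. Ten may suffice for an effect near 1 SD in one pair, or for about half an SD in an averaged contrast with pooled error.

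A reader might also take 13-14% as the error rate of the plan as written. It is not. Section 11 speaks of surgical and control groups, which this crossover does not have, and never says which conditions its signed-rank test pairs. Applying that test to distal versus stomach is our reading, and three pairs are not the least that the Primary Aim requires, since one averaged contrast covers it.

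Conversely, a reader might suppose that hormones are safe because rank-sum is conservative on same-subject data. That depends on the correlation: at 0 or 0.3, three tests still exceed 5%.

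Finally, the choice between an averaged and a protein contrast, and the choice of test, are design preferences. That is fair, and they are left to the sponsor.

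**Conclusion.** The point holds and should be fixed before data are seen. The stated 80% does not belong to the declared primary endpoint, its inputs are absent, and no primary contrast or multiplicity rule exists. These facts rest on the text alone.

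The sizes are conditional: the false-positive figures on the tests and correlations assumed above, and the detectable effect of about 1.0 SD on normal differences, ten completers and one paired comparison. That effect cannot be put in mm or kcal, because the plan gives no SD. For VAS there is a further gap: 5.3 names no item, time point or summary measure, so even the SD has no defined variable.

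**What to change.** 1. **Endpoint.** Either name ad libitum energy intake as primary in 5.3, or keep VAS appetite and specify its item, time point and summary measure. In the second case, state in 5.5 that the 80% refers to intake only and that ten completers detect about 1.0 SD of the paired difference on VAS.
2. **Contrast.** Before data are seen, name one primary distal-minus-stomach contrast on that endpoint. The average over the three macronutrients is the one contrast that covers the Primary Aim. The high-protein pair is an alternative. The choice is the sponsor's.
3. **Multiplicity.** Test the remaining within-macronutrient contrasts by Holm, and only if the primary contrast is significant. Make no confirmatory claim for other outcomes.
4. **Section 5.5.** State the test, contrast, assumed difference and SD (kcal or mm) actually used. If these cannot be recovered, give the detectable effect in SD, say which SD it is, and state the normality assumption.
5. **Losses.** State that 10 means completers for the primary contrast, and whether withdrawn subjects are replaced.

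**Cost.** A text amendment to 5.3-5.5 and 11 with ethics committee approval under 13.1, and no extra subjects apart from any replacements. The power stated for non-primary contrasts becomes less favourable. At the first Holm step, 80% power needs about 1.14 SD (paired t) to 1.22 SD (signed-rank) if two contrasts remain (0.05/2), or about 1.22 to 1.30 SD if three remain (0.05/3). With an averaged primary contrast, a protein-only effect of 1.0 SD would be declared for protein in only about 19-27% of trials (assumed correlation 0.5 to 0), against 78% with a protein primary.
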